Patients determined to be eligible for the study by the patient's clinical provider (and per our previously defined criteria) will be recruited to enroll in the project within the first 24 hours of their hospital admission (i.e. 24 hours following the documented H&P Note). They will be offered the opportunity to consent to enrollment in the study and will be assigned by the study team into either the intervention (RibFx belt +current standard of care) (n=35 subjects) or control (current standard of care) arm (n=15 subjects) in a quasi-experimental prospective design: untreated control group with dependent pretest and posttest samples. In this manner, the intervention arm will be both compared to themselves (pretest vs. posttests) as well as to a control group not exposed to the intervention.

Patients upon enrollment in the study will undergo an initial assessment that will include their baseline pain scores, narcotic

consumption, incentive spirometry scores, and the subjective self-reported results of their questionnaire (the pre-test questionnaire- see attached). Patients will continue to be scored on objective (incentive spirometry results, opioid pain medicine consumption) and subjective variables (pain scores) during their hospital course. Between 24-48 hours after enrollment, they will be prompted to again complete a similar 2nd questionnaire post-test (if they are discharged from the hospital at this point in the time course, they will be sent home with the questionnaire and prompted to complete it at home, or asked for an agreed upon time and day for study staff to call the patient to complete the questionnaire over the phone). At their follow up appointment in trauma clinic (which will be coordinated by the research team to be as close as possible to 3 weeks post injury), they will have the opportunity to again voluntarily complete a final short questionnaires (post-test) that assess their pain control and respiratory function over the last 3 weeks. If the patient does not plan to follow up in trauma clinic (or is not asked to), we will ask the patient for an agreeable time and day to call the patient and administer the questionnaire over the phone. At this point, their involvement in the trial will be complete.

All aspects of data collection will be performed only by approved members of Key Personnel.

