All patients will undergo initial "Pre-test" testing which will include baseline pain scores (1-10 traditional pain scale), initial narcotic consumption (in MME) for first 24 hours of hospitalization, maximum incentive spirometry score for first 24 hours of hospitalization, and pre-test questionnaire result (see attached questionnaire #1). As the study continues their relevant data will be collected, including both objective (incentive spirometry scores, opioid pain medication consumption, incidence of atelectasis and pneumonia) and subjective (pain scores, survey result) clinical data. Concurrently, we will complete the trial with the intervention (RibFx belt) phase in which participants will be enrolled in the interventional arm of the study. The objective and subjective data will be collected in an identical fashion- the only difference between groups will be that this group will have been fitted with the RibFx belt for their hospital course and discharge.

The participants (both in the control and interventional groups) will again be asked to complete essentially the same brief surveys in a post-test fashion at two set time points: between 24-48 hours after initial enrollment in the study (Questionnaire #2)(if patient has been discharged at this point, they will be sent home with this survey and instructed when to complete, or facilitated completion by calling the patient at this time), and at 3 weeks post-injury (this will be done at their clinic visit, assuming they are not still admitted to the hospital at this time point).

Patients will also be sent home with a work-book to record their incentive spirometry scores and pain scores (all patients will be sent home with an incentive spirometer, and all patients in the interventional group will be sent home with their Ribfx belt).

[figure not shown]

The following schematic will be used for enrollment group assignment in the study (n=50 total participants):

During the chart review portion of the study, patients who have authorized to have their medical records reviewed will have their post-traumatic records reviewed for the following diagnoses or conditions: respiratory failure, tracheostomy requirement, pneumonia, tube thoracostomy (chest tube), epidural use, intubation rates, hospital length of stay, and mortality.

[figure not shown]
The following schematic represents the patient/subject trial course:

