Each patient in the interventional arm will be fitted with a RibFx orthosis belt, which is to be worn during the majority of their day (excluding showering/bathing). It will be encouraged (though not mandatory) to wear at night. Patients in both the control and interventional arm will be expected to participate in pulmonary hygiene / toilet exercises with guided and independent incentive spirometry as per our normal routine and standard of care. There are no other interventions or procedures that the patients will be subjected to for the research trial- other procedures/interventions will be performed only if the clinical care team feels they are indicated.

For research involving survey, questionnaires, etc.: *Describe the setting and the mode of administering the instrument and the provisions for maintaining privacy and confidentiality. Include the duration, intervals of administration, and overall length of participation. (describe and attach all instruments)*

Not applicable

Patients will be assessed with three short questionnaires in a pretest , posttest fashion at both the onset of the study, 24-48 hours after enrollment, and at their follow-up appointment 3 weeks after (2 post test questionnaires). The initial evaluation will occur on initial assessment prior to placement of the rib belt (or, for the control/ non-intervention group, at the onset/first 24 hours of the study).

Each of the questionnaires is essentially the same with only brief modifications made in the first two questions to make them appropriate for the timing during the clinical course. However these are all attached (see Questionnaire 1,2, and 3). Questionnaires 2 and 3 may be facilitated over the phone if the patient is discharged before the defined time frames are met.

Patients in both the intervention and control arms will present in post-admission follow up at a time period of 3 weeks post injury (range, 2-4 weeks) following their hospital admission, and will be asked to fill out a brief survey regarding their respiratory function and pain control. This survey will also inquire into compliance with the use of incentive spirometer, and compliance with the use of the RibFx belt (for patients in the intervention arm). If patients are not asked to present to trauma clinic for follow up, or if a patient does not intend to follow up, we will aim to complete this questionnaire over the phone in the same time frame.

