Adverse events will be reported as soon as they are identified to the research protections office and will be subject to thorough review. The affected patients, if applicable, will be notified regarding this adverse event. If needed, the clinical care team will provide any medical care related to this adverse event. Necessary changes to prevent the recurrence of such an event will be implemented with the assistance of the review board, and if necessary (for serious adverse events) the trial may be terminated early for patient safety.

Withdrawal Procedures: Define the precise criteria for withdrawing subjects from the study. Include a description of study requirements for when a subject withdraws him or herself from the study (if applicable).

Patients will be eligible to withdraw from the study at any time if they chose to. This includes participants in both the control and intervention arms of the trial. Subjects will be asked to provide a reason for withdrawal (such as intolerance or difficulty with the rib belt, worsened pain associated with the rib belt, personal preference, difficulty complying with study rules, etc.), but patients are also free to withdraw without providing a reason.

A patient may be deemed no longer eligible for inclusion in the trial by the research team (such as if the patient undergoes rib fixation surgery). These patients will be removed from the trial and will be notified of the reason for their removal.

Sources of Materials: Identify sources of research material obtained from individually identifiable human subjects in the form of specimens, records or data. Indicate whether the material or data will be obtained specifically for research purposes or whether use will be made of existing specimens, records or data.

Sources of materials will principally be derived from studies, images, tests that the patient is already undergoing as part of the standard of care for rib fracture treatment. The only additional test obtained solely for research purposes is the pre-test and post-test questionnaires. X-rays and imaging tests analyzed will be obtained for clinical use and NOT solely for research purposes, however the images will undergo additional analysis by a blinded radiologist participating in the study. This will not incur any additional costs or radiation to the patient.

DRUG AND DEVICE INFORMATION

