Subjects targeted for the study are those that would benefit most from the intervention (Rib belt)- patients with traumatic rib fractures. In order to determine if the belt has efficacy in this population, we must utilize the belt in this target population. Patients at the extremes of age (<18 or >80 years old) have been ruled out as they may create unreasonable confounding when measuring the relevant study outcomes, as well as potentially creating issues with autonomy and consent processes. There are also other exclusion criteria as dictated below.

Vulnerable Populations: Explain the rationale for involvement of special classes of subjects, if any. Discuss what procedures or practices will be used in the protocol to minimize their susceptibility to undue influences and unnecessary risk (physical, psychological, etc.).

Not applicable

Number of Subjects: What is the anticipated number of subjects to be enrolled at UVM/UVM Medical Center and in the case of a multi-center study, with UVM/UVM Medical Center as the lead, the total number of subjects for the entire study.

The current anticipated number of subjects is 35 patients in the intervention arm, and 15 in the control arm of the study, for a total of 50 patients. All these subjects will be enrolled at UVMMC.

Inclusion/Exclusion Criteria: Eligibility and ineligibility criteria should be specific. Describe how eligibility will be determined and by whom. Changes to the eligibility criteria at a later phase of the research have the potential to invalidate the research.

Inclusion Criteria:

Adult person age 18-80 admitted with at least one acute traumatic closed rib fracture to the University of Vermont Medical Center

Exclusion Criteria:

Pediatric (<18 year old) and Geriatric (>80 year old) patients

Patients who are intubated on arrival or within first 24 hours of admission or with Glasgow Coma Scale (GCS) < 14 (altered or depressed consciousness)

Pregnant patients

Patients who undergo operative rib fixation for their rib fractures (such as open reduction internal fixation, or rib plating)
 Patients with chest wall deformity, lacerations, burns, or soft tissue injuries that preclude placement of the RibFx belt
 Patients with an additional mechanism of injury that would create severe distracting pain, as determined by the admitting team.
 Isolated 1st rib or 2nd rib fractures

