Payment for participation: Describe all plans to pay subjects, either in cash, a gift or gift certificate. Please note that all payments must be prorated throughout the life of the study. The IRB will not approve a study where there is only a lump sum payment at the end of the study because this can be considered coercive. The amount of payment must be justified. Clarify if subjects will be reimbursed for travel or other expenses.

Not applicable

There will be no payment or financial incentive for the subjects to participate. The medical device RibFx belt will be provided to the intervention group free of charge, and they will be allowed to keep the medical device upon discharge (MSRP \$125 USD).

Collaborating Sites. When research involving human subjects will take place at collaborating sites or other performance sites when UVM/UVM Medical Center is the lead site, the principal investigator must provide in this section a list of the collaborating sites and their Federalwide Assurance numbers when applicable. (agreements may be necessary)

Not applicable

Single center study at the University of Vermont Medical Center main campus (Burlington, VT). No collaborating centers or satellite/off-site locations.

INFORMED CONSENT

Consent Procedures: Describe the consent procedures to be followed, including the circumstances under which consent will be obtained, who will seek it, and the methods of documenting consent. Specify the form(s) that will be used e.g. consent (if multiple forms explain and place identifier on each form), assent form and/or HIPAA authorization (if PHI is included). These form(s) must accompany the protocol as an appendix or attachment.

Note: Only those individuals authorized to solicit consent may sign the consent form confirming that the prospective subject was provided the necessary information and that any questions asked were answered.

Consent will be obtained at the time of enrollment (during the first 24 hours of the patient's inpatient admission/observation, on their initial encounter for acute traumatic rib fracture) and consent will be obtained at the bedside by one of the members of the research team.

All documentation of consent observation/supervision will be kept in the study regulatory binder.

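### Rib fixation and intubation within 24 hours of admission are exclusions that can be met after enrolment, and no analysis population keeps the affected patients in.

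*Combined protocol and SAP*

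**What the plan says.** **Enrolment.** The opening study summary says patients "will be recruited to enroll in the project within the first 24 hours of their hospital admission", counted from the documented admission note. Consent Procedures agrees: "Consent will be obtained at the time of enrollment (during the first 24 hours of the patient's inpatient admission/observation".

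**Exclusions.** Inclusion/Exclusion Criteria lists "Patients who are intubated on arrival or within first 24 hours of admission" and "Patients who undergo operative rib fixation for their rib fractures". The second has no time limit.

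**After enrolment.** Withdrawal Procedures says "A patient may be deemed no longer eligible for inclusion in the trial by the research team", gives rib fixation surgery as an example, and continues: "These patients will be removed from the trial and will be notified of the reason for their removal".

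**Outcomes.** The chart review in Study Design covers respiratory failure, tracheostomy and pneumonia, and also "epidural use, intubation rates, hospital length of stay, and mortality". Ventilator days are extracted as well. The hypothesis under Purpose has two halves: better pain control, and no significant respiratory impairment or increase in respiratory complications.

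**Belt timing.** The questionnaire section says "The initial evaluation will occur on initial assessment prior to placement of the rib belt". It gives no clock time. Study Design defines the pre-test opioid total and maximum spirometry over the first 24 hours of hospitalization.

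**Analysis set.** Statistical Considerations defines no analysis population, no rule for missing data, and no rule for data from removed patients.

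**The concern.** Eligibility should rest on what is known when the patient enters. Here two criteria rest on events that can come later, and both events bear on what the trial measures. Intubation is a listed chart outcome. Fixation is surgery on the fractures whose pain is being scored. If patients leave the analysed group because of such events, the result describes a subgroup defined by its own later course.

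The exposure is greatest in the comparison that the protocol calls its principal aim, belt patients against their own baseline. Nothing there offsets the loss. If the removed patients would have done worse than the rest, the pre-post change looks larger and the complication rate lower than among everyone enrolled. The decision to remove is also open-ended, since fixation is only an example, and it belongs to a research team that is not described as blinded. The only blinding in the document is that of the radiologist.

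**Working it through.** **1. Timing of the two exclusions**

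| Rule | When it can be met | Relation to enrolment (hours 0–24) |
|---|---|---|
| Intubation | Arrival to hour 24 | Overlaps the whole enrolment window |
| Rib fixation | Any time | Can follow enrolment without limit |

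Therapeutic Alternatives already keeps operative candidates out at entry. The fixation wording in Withdrawal Procedures therefore acts only on patients already enrolled.

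**2. When the belt goes on: two readings**

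- *Fitted soon after an early enrolment.* The questionnaire section requires only that the initial evaluation comes first. A patient could then be intubated on the belt before hour 24 and meet the exclusion.
- *Fitted after the full pre-test.* If the 24-hour opioid and spirometry baseline must be complete first, any intubation that meets the exclusion precedes the belt, and no on-belt event is lost through that rule.

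The text supports either reading. The fixation rule is unaffected by the choice.

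**3. The plan's own power figure**

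Inputs from Statistical Considerations: MPQ PRI mean 28, SD 16, 20% decrease, within-subject correlation 0.8, two-sided alpha 0.05.

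- Difference = 0.20 × 28 = 5.6.
- SD of change = 16 × √(2 × (1 − 0.8)) = 10.12.
- Standardised effect = 5.6 / 10.12 = 0.553.
- Paired t test (noncentral t): 83.4% at n = 30 (stated 83%) and 88.9% at n = 35 (stated 88%).

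The stated figures are reproduced. They are not in dispute.

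**4. Illustration for pain: k of 35 belt patients removed**

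k is an assumption. Suppose the other 35 − k improve by 5.6 on average and the k removed patients would have shown no change. Then, with p = (35 − k)/35:

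- Patients remaining: mean decrease 5.6, that is 20%, whatever k is.
- All 35: mean decrease = 5.6p; variance of change = 10.12² + p(1 − p) × 5.6².

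For k = 3: p = 0.914; mean = 5.12; SD = √(102.4 + 2.46) = 10.24; effect = 0.50; power 82.0%.

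| k | Decrease, remaining | Decrease, all 35 | Power, all 35 |
|---|---|---|---|
| 1 | 20% | 19.4% | 86.8% |
| 3 | 20% | 18.3% | 82.0% |
| 5 | 20% | 17.1% | 76.3% |

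**5. Illustration for early intubation in the belt arm**

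The counts are assumed, and so is that every such patient leaves the denominator. The upper limits are from exact two-sided 95% intervals: the 97.5% quantile of Beta(k + 1, 35 − k) for k/35, and 1 − 0.025^(1/n) for 0/n.

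| All enrolled | Upper limit | After removal | Upper limit |
|---|---|---|---|
| 1/35 = 2.9% | 14.9% | 0/34 | 10.3% |
| 2/35 = 5.7% | 19.2% | 0/33 | 10.6% |
| 3/35 = 8.6% | 23.1% | 0/32 | 10.9% |

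**6. Chance that the rules affect anyone**

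For an assumed probability q that a belt patient meets a removal rule, the chance of at least one among 35 is 1 − (1 − q)^35. This gives 30%, 51%, 83% and 97% for q = 1%, 2%, 5% and 10%.

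**The case against.** The strongest defence is the target population. Both objectives concern non-operatively managed fractures, and operative candidates are barred, so excluding fixation follows from the question. That supports screening at entry. It does not support dropping an enrolled patient once surgery has happened, because who remains then depends on the course after enrolment.

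A reader might infer that the rules erase respiratory failures on the belt. The documents do not support this. Fitting before hour 24 is possible but not stated, and the 24-hour baseline allows a later fitting. The time allowed for deciding on consent, up to 24 hours, can shorten the overlap further. Intubation after hour 24 and respiratory failure without intubation trigger no exclusion and remain outcomes. Withdrawal Procedures does not name intubation, and it does not say that data already collected are discarded. Adverse events must still be reported to the research protections office, although that does not settle the analysis denominator.

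Nor can one say that only patients who did well would remain, since poor pain control and later complications lead to no removal. Fixation is not defined as a treatment failure, and no reasons for conversion are given. For belt versus control, the rules apply to both arms and the direction of any bias is not determined. The protocol also says that comparison is not powered and presents the trial as a pilot. All of this narrows the point. The explicit removal rule and the missing analysis population still stand.

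**Conclusion.** The concern holds in a limited form. The fixation part rests on explicit text: enrolled patients are removed for an event after enrolment, by discretion, with nothing to keep them in the analysis. The intubation part rests on an explicit overlap of windows. Whether it reaches on-belt events depends on a fitting time that the document leaves open.

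The size cannot be fixed, because no intubation, fixation or dropout rate is given. On the assumed counts, one to three removals would turn an early intubation rate of 2.9% to 8.6% into zero and lower the exact upper limit from 14.9%–23.1% to 10.3%–10.9%. For pain, one to five removed patients with no change would leave a reported 20% decrease where all enrolled show 19.4% to 17.1%. These figures also assume that removed patients leave the denominator, on which the plan is silent. An upward shift in the pre-post result further assumes that removed patients would have done worse than the rest.

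**What to change.** - Inclusion/Exclusion Criteria: judge both criteria on what is known at enrolment, that is, already intubated, or already a candidate for or planned to have fixation.
- Withdrawal Procedures: replace the removal rule. Every enrolled patient stays in the analysed group and in the adverse-event counts, and chart outcomes continue to be collected unless consent is withdrawn.
- Statistical Considerations: define that analysis population. Report intubation and fixation after enrolment by arm, with time from belt placement in the belt arm. Prespecify how pain and opioid data after these events are handled, and add a sensitivity analysis limited to patients who stayed non-operative, which preserves the link to the stated objectives.
- Study Design and the questionnaire section: reconcile the 24-hour baseline window with the time of belt placement.

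The cost is a few amended sentences and no extra patients. The downside is that a few retained patients may have missing questionnaires, or answers affected by surgery. The changes should be made before any results are seen, because a choice of analysis set made afterwards would not be credible.

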Secondary objectives: Compare pulmonary hygiene and function amongst patients with non-operatively managed traumatic rib fractures via incentive spirometry scores and incidence of post-traumatic pneumonia and radiological evidence of atelectasis incidence

METHODS AND PROCEDURES

Study Design: *Describe the research design, including a description of any new methodology and its advantage over existing methodologies.*

Per Jeffords Institute for Quality Data, there were 190 patients admitted to the Acute Care Surgery (Trauma) service at the University of Vermont Medical Center during the year 2016. Assuming that these numbers remain fairly static overtime as they have in the past, we would expect approximately 16 patient admissions per month with the diagnosis of rib fracture (seasonal fluctuations do exist with more traumatic admissions during the summer months). The goal time period for the trial would be to conduct this trial during the summer, with a goal of 50 total patients. We would therefore expect an enrollment period (data collection phase) of approximately 3 months.

During the study (following appropriate IRB approval), appropriate patients will be recruited both to the control arm of the study and the intervention/comparison arm in a specified / non-randomized sequence as seen in the schematic below (First 5 patients control, next 5 patients intervention, next 5 patients control, next 5 patients intervention, next 5 patients control, final 25 patients intervention). Control arm will include 15 total patients. All will be consented to the study upon admission (first 24 hours of index hospitalization for injury) with full knowledge that they will either be undergoing no intervention other than receiving the current standard of care for rib fracture care per our institution's standard, and if assigned to the rib belt group, expected to wear the rib belt during their recovery.

The current standard of care for rib fractures at our institution is as follows: includes oral and IV analgesia and other multimodal pain control as appropriate, including muscle relaxants such as methocarbamol (robaxin) unless there is a contraindication, pulmonary hygiene/toilet and respiratory care (including frequent evaluations by physicians, respiratory therapists, and nursing staff, early mobilization, and monitoring for pulmonary complication (via vital signs, pulse oximetry, oxygen requirement, chest imaging if appropriate).

[figure not shown]

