Patients who are first identified by the clinical care team (The Acute Care Surgery/ACS/ Trauma Surgery team at UVMC) as meeting the desired inclusion criteria for the trial will be offered the opportunity to participate in the trial and appropriate clinical materials will be given by a member of the research team. There will be no advertisements, mailers, or other relevant recruitment materials other than an informational pamphlet, a device pamphlet, and the appropriate consent/authorization forms. These items are attached with the relevant research forms.

FINANCIAL CONSIDERATIONS

Expense to Subject: If the investigation involves the possibility of added expense to the subject (longer hospitalization, extra studies, etc.) indicate in detail how this will be handled. In cases where the FDA has authorized the drug or device company to charge the patient for the experimental drug or device, a copy of the authorization letter from the FDA or sponsor must accompany the application. Final approval will not be granted until the IRB receives this documentation.

There are very limited circumstances under which study participants may be responsible (either directly or via their insurance) for covering some study-related expenses. If the study participant or their insurer(s) will be billed for any portion of the research study, provide a justification as to why this is appropriate and acceptable. For example, if the study involves treatment that is documented standard of care and not investigational, state so. In these cases, the protocol and the consent should clearly define what is standard of care and what is research.

The research team does not anticipate that participation in the trial will result in any additional hospital time or expense. The actual RibFx belt will be provided, free of charge to the patient (actual retail value \$125 USD). All other interventions and modalities will be per the current standard of care for the treatment of rib fractures- patients will continue to be billed for the rest of their hospital care. In that (expectedly) extreme rare event that at any point during the trial it became apparent that the device has caused a medical complication necessitating additional treatment, this medical care will be provided without billing the patient for those services.

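### The fixed, unconcealed order of arms means the next arm could be known when two judgement-based exclusions are applied, so belt and control slots could be screened differently

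*Combined protocol and SAP*

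**What the plan says.** **Allocation.** Methods and Procedures, Study Design, recruits patients "in a specified / non-randomized sequence as seen in the schematic below". The order is "First 5 patients control, next 5 patients intervention, next 5 patients control, next 5 patients intervention, next 5 patients control, final 25 patients intervention". In the opening study summary, patients who are offered consent "will be assigned by the study team into either the intervention (RibFx belt +current standard of care) (n=35 subjects) or control" (15 subjects).

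**Eligibility.** The opening summary states: "Patients determined to be eligible for the study by the patient's clinical provider (and per our previously defined criteria) will be recruited". The Recruitment section concerns "Patients who are first identified by the clinical care team" as meeting the criteria. Under Exclusion Criteria, two items have no scale, threshold or definition:

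- "Patients with an additional mechanism of injury that would create severe distracting pain, as determined by the admitting team"
- "Patients with chest wall deformity, lacerations, burns, or soft tissue injuries that preclude placement of the RibFx belt"

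**Role of the controls.** Statistical Considerations assumes that pain improves with time whatever the treatment, and uses the 15 controls to show that change. It also says that the study is not powered to compare the arms. The principal aim is the pre-post comparison within the 35 belt patients.

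**What is not described.** There is no concealment of the order, no eligibility sign-off before the slot is revealed, and no screening log. The only blinding mentioned is that of the radiologist who grades the images.

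**The concern.** An eligibility criterion protects the comparison only if it is applied without regard to the arm that the patient will enter. Here the arm of each slot is settled before the patient arrives, and two exclusions depend on how a clinician reads the case. The belt-placement item invites this most. It has a practical consequence only when a belt must be fitted, so a borderline chest wall could be passed in a control slot and failed in a belt slot. The distracting-pain item and the consent conversation are open to the same influence.

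At stake is whether the 15 controls show the recovery of patients like the 35 who wear the belt. If the two sets of slots are filtered differently, the controls lose that role, and the pre-post fall in the belt arm cannot be separated from natural recovery. This differs from the question of where the controls fall in calendar time: it would remain if control slots were spread over the whole enrolment period.

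**Working it through.** 1. **The plan's own figure.** Inputs from Statistical Considerations: MPQ PRI mean 28, SD 16, 20% decrease, within-subject correlation 0.8, two-sided 0.05. Target change = 0.20 × 28 = 5.6. SD of the difference = 16 × √(2 × (1 − 0.8)) = 10.12. Standardised effect = 5.6 / 10.12 = 0.553. A paired t test (noncentral t) gives 83.4% power with 30 patients and 88.9% with 35, against the stated 83% and 88%. The figures reproduce within a point and do not depend on this concern.

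2. **Predictability.** The order gives 5 + 5 + 5 = 15 controls and 5 + 5 + 25 = 35 belts. Someone with the order and the running count knows the next arm for 50 of 50 slots. For the last 25, it is enough to know that the control group is full. With a randomly permuted list of the same 15 and 35 slots and known totals, always guessing belt is right 35/50 = 70% of the time. Guessing whichever arm has more slots left is right about 71% of the time (simulation).

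3. **Illustrative size.** Assume that baseline MPQ PRI is Normal(28, 16), that a share p with the most pain is kept out of belt slots but not control slots, and that the belt has no effect. The fall in the belt arm's baseline mean is 16 × φ(z) / (1 − p), where z is the upper-p normal quantile.
   - p = 0.10: z = 1.28, φ = 0.1755; 16 × 0.1755 / 0.90 = 3.12 points.
   - p = 0.20: z = 0.84, φ = 0.2800; 16 × 0.2800 / 0.80 = 5.60 points.

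4. **What this does to each analysis**, with correlation 0.8 and equal SDs before and after:

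| Analysis | Formula | p = 0.10 | p = 0.20 |
|---|---|---|---|
| Post-test scores, unadjusted | 0.8 × shift | 2.50 | 4.48 |
| Change scores | (1 − 0.8) × shift | 0.62 | 1.12 |
| Post-test adjusted for baseline | none in this model | 0 | 0 |

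On unadjusted post-test scores the bias favours the belt. On change scores it runs against the belt, because patients who start lower fall less.

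5. **Which row applies.** The plan does not settle this. Statistical Considerations names an unpaired t test for continuous survey items. The stated design is a dependent pretest-posttest one. Study Design says that differences in radiological severity will be accounted for, but no adjustment model is given.

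**The case against.** The case on the other side is substantial.

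- **Foreknowledge is not documented.** A reader might infer that the admitting team knows the next arm. No section says that it is told the order or the count. The clinical team judges eligibility, the study team assigns, and the consent wording covers both assignments. This stands: what the documents support is that the arm could be known, because nothing is said to prevent it.
- **The direction is not given.** Both exclusions are written for all patients. Steering painful cases towards belt slots is as plausible as steering them away. Simple chest-wall tenderness is not an exclusion. This stands.
- **The illustration is a loose proxy.** The distracting-pain item concerns pain from another injury, whereas MPQ PRI is used in the plan as a chest-wall pain score and is not named among the trial's own measures. This stands, so the figures show only how much the choice of analysis matters.
- **Adjustment is possible.** Baseline pain, first-24-hour narcotic use and a questionnaire are collected in both arms, before the belt is placed in the belt arm. Belt compliance is surveyed, reasons for withdrawal are requested, and images are graded blind. It would be wrong to say that nothing relevant is recorded. Still, these data describe enrolled patients only. Without a log, the reasons for keeping others out are unrecorded and cannot be adjusted for.
- **The principal analysis is within the belt arm.** This limits the harm but does not remove it, since the plan relies on the controls to interpret the pre-post change.

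**Conclusion.** The concern holds as a weakness that the design permits, not as a bias shown to occur. It rests on two facts in the text (a fixed written order and two undefined exclusions) and one inference (that without concealment the order could reach those who judge eligibility or seek consent). The main casualty is the control comparison. The pre-post analysis is touched less, through who enters the belt sample.

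Direction and size are unknown. Under the assumed 10% to 20% differential exclusion, the bias ranges from zero with baseline adjustment, through about 0.6 to 1.1 points on change scores, to about 2.5 to 4.5 points on unadjusted post-test scores.

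A reader might note that the 20% case gives a 5.6-point baseline gap and conclude that the bias equals the plan's target effect. That does not follow: one is a between-arm difference at baseline, and the other is a within-patient change. The match should carry no weight.

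The change is worth making because it is cheap and removes certain foreknowledge, not because a large bias has been demonstrated.

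**What to change.** 1. Have the clinical provider complete and time-stamp an eligibility checklist that includes both judgement items, worded operationally and applied identically whatever the arm. Have consent signed before the slot is revealed.
2. Keep the order and the running count from those who judge eligibility. Preferably, replace the fixed order with a concealed, computer-permuted order of the same 35 belt and 15 control slots, opened by existing Key Personnel after consent.
3. Keep a screening log of every exclusion, by reason and by the slot then open, with the slot added afterwards by someone who does not judge eligibility.

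**Cost.** Protocol wording, a checklist, a log and one set of sealed assignments, with no extra patients or staff. Belts and staff time could no longer be planned by block. The permuted order changes the declared non-randomised sequence, so the design description would need amending. If the investigators wish to keep that sequence, items 1 and 3 and the first half of item 2 still address most of the concern. The 35:15 totals leave belt the likelier guess (about 71% correct), so some predictability remains.
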